#### **9.4.10 Dosing Changes Due to AEs**

Dose interruptions are allowed should a subject experience intolerable treatment-related adverse events (e.g., pruritis) on study. In cases where the Investigator feels a dose interruption is warranted, the subject should be instructed to interrupt study drug application to allow symptoms to resolve. Subjects should be instructed to return to the twice daily application regimen within 2 days of dose interruption.

Dosing interruptions are to be recorded in the subject diary as a missed dose.

Study drug must be discontinued if an adverse event is deemed persistent and if continuation of study drug would not be in the best interest of the subject.

Refer to [Section 10.3](#) for further information regarding discontinuation of study drug or early withdrawal.

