### **11.3 Exposure and Compliance**

The extent of exposure to study drug in each treatment group will be summarized by total number of days of exposure, total number of applications, number of missed applications and number and percentage of subjects who are compliant. A subject will be considered compliant

with the dosing regimen if the subject applied 80% to 120% of the expected number of applications while enrolled in the study.

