If the Date of First Application = Date of Last Application, then

$$\text{Total Applications} = \text{Expected Applications on Date of First Application} \\ - \text{Missed Applications} + \text{Extra Applications.}$$

Treatment compliance will be based on the expected number of doses given the treatment period duration. Treatment period duration will be computed from the date of first application of Olumacostat Glasaretil Gel, 5.0% (from ACN03/ACN04 or ACN05) and the date of last application.

Then treatment period duration may be calculated as:

$$\text{Treatment Period Duration} = \text{Date of Last Application} - \text{Date of First Application} + 1.$$

Missed applications due to treatment-related AEs will be considered when determining the expected number of doses for each subject. If a treatment-related AE (regardless of location) requires interruption of study drug during the treatment period, missed applications during the AE (onset date to resolution date) will be deducted from the expected number of doses. Therefore, the expected number of applications will be calculated as:

$$\text{Expected Applications} = 2 * (\text{Treatment Period Duration} - 2) \\ + \text{Expected Applications on Date of First Application} \\ + \text{Expected Applications on Date of Last Application} \\ - \text{Applications Missed Due to a Treatment-Related AE.}$$

Percent compliance will be calculated from total number of applications and total number of expected applications as follows:

$$\text{Percent Compliance} = 100 * (\text{Total Applications} / \text{Expected Applications}).$$

Percent compliance will not be calculated for subjects who are lost to follow-up.

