### **8. CHANGES IN THE PLANNED ANALYSES**

No changes to planned analyses.

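### SAP 6.8.1 deducts every application missed between onset and resolution of a qualifying related AE, not only those missed because of it, so percent compliance is biased upward

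*SAP*

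**What the plan says.** Protocol 11.3 counts a subject as compliant "with the dosing regimen if the subject applied 80% to 120% of the expected number of applications while enrolled in the study". It does not define the expected number and does not mention AEs.

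SAP 6.8.1 keeps the 80–120% criterion and defines the expected number in three steps:

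- The lead sentence states the purpose: "Missed applications due to treatment-related AEs will be considered when determining the expected number of doses for each subject".
- The operative rule has a trigger, "If a treatment-related AE (regardless of location) requires interruption of study drug during the treatment period", and a consequence, "missed applications during the AE (onset date to resolution date) will be deducted from the expected number of doses".
- The formula then subtracts a term labelled "Applications Missed Due to a Treatment-Related AE".

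The numerator, total applications, already has every missed application subtracted, whatever its cause.

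On interruptions, Protocol 9.4.10 says "Subjects should be instructed to return to the twice daily application regimen within 2 days of dose interruption" and "Dosing interruptions are to be recorded in the subject diary as a missed dose". SAP 8 states "No changes to planned analyses".

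**The concern.** The lead sentence and the formula label speak of misses caused by the AE. The operative rule selects misses by date. The interruption decides only which AEs qualify; the AE's onset and resolution dates decide which misses are deducted. A long, low-grade related AE with one short interruption would thus also excuse doses forgotten weeks before or after that interruption.

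A miss removed from both numerator and denominator no longer lowers the ratio. If all of a subject's misses fall inside the window, the result is 100% however many there were. The inflation occurs only in subjects with related AEs that led to interruption. Those are the subjects in whom a long-term safety study most needs to see how much of the regimen was actually followed.

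**Working it through.** The documents give no worked compliance figure, so there is nothing to reproduce. The check applies the SAP 6.8.1 formulas to an illustrative subject.

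**Inputs from the documents**
- Treatment of 36 weeks (SAP 4.1): 36 × 7 = 252 days, so last date − first date = 251.
- Two applications a day (SAP 6.8.1).
- Compliance threshold of 80% (SAP 6.8.1, Protocol 11.3).

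**Assumptions, not in the documents**
- Two applications expected on each of the first and last dates, and no extra applications.
- One related AE from Day 20 to Day 240, with one 2-day interruption (4 applications missed).
- 120 other missed applications inside the AE dates and none outside, so 124 in all. The window is 221 days, or 442 scheduled applications, so 124 misses fit. At two misses a day they would need at least 124 / 2 = 62 days.

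**General form.** Let E be scheduled applications, M all missed and W those missed inside the AE window. With no extra doses,

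compliance = 100 × (E − M) / (E − W).

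When W = M this is 100% for any M.

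**The illustrative subject**
- Total applications = 2 × (251 − 1) + 2 + 2 − 124 = 380.
- Scheduled applications before any deduction = 2 × (252 − 2) + 2 + 2 = 504.

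| Deduction | Expected | Compliance | At least 80%? |
|---|---|---|---|
| SAP rule, all 124 misses in the window | 504 − 124 = 380 | 380 / 380 = 100% | yes |
| Only the 4-application interruption | 504 − 4 = 500 | 380 / 500 = 76.0% | no |
| None | 504 | 380 / 504 = 75.4% | no |

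**How much deduction changes the classification.** The subject reaches 80% when expected applications fall to 380 / 0.80 = 475, a deduction of 504 − 475 = 29. That is 25 more than the assumed interruption. The window need not hold all 124 misses to turn a non-compliant subject into a compliant one.

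**Sensitivity to the interruption**
- Three such interruptions (12 applications) over 36 weeks: 380 / (504 − 12) = 380 / 492 = 77.2%, still below 80%.
- A 12-week treatment period (168 scheduled, 42 missed, 126 taken): 126 / 168 = 75.0% with no deduction; 126 / (168 − 4) = 76.8% with one interruption; 126 / (168 − 12) = 80.8% with three. In the last case the narrower rule also calls the subject compliant, although the SAP rule still reports 100%.

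**The case against.** The strongest reply is that the operative sentence stands between two statements limited to misses caused by the AE, so a narrow reading may have been intended. That is possible. But the date window is the only operational definition the SAP gives. The protocol describes no field that gives the reason for a missed application or separates an interruption from any other miss. A programmer would apply the window. At the least, rule and label disagree.

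Four stronger readings are tempting, and the documents do not support them.

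- **That the SAP contradicts Protocol 11.3.** That section never defines the expected number, and Protocol 11.1 leaves the description of the analyses to the SAP. The AE deduction is an undisclosed addition to a silent text.
- **That an interruption cannot exceed 2 days.** Protocol 9.4.10 gives an instruction for subjects, not a recorded maximum, and it allows interruptions in the plural. The 4 applications above are therefore an assumption. Nor does 9.4.10 conflict with the SAP: one instructs subjects, the other sets an accounting window.
- **That an AE unresolved at exit makes the deduction unlimited.** The SAP states no end date for that case, but only missed applications within the treatment period can be deducted, so the last application bounds it in effect.
- **That reported exposure as a whole is overstated.** SAP 6.8.1 also summarises days of exposure, total applications, missed applications, amount of drug used and amount per day, none with an AE deduction.

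Two further points stand. The example is constructed, and extreme cases are limited by counselling for significant dosing deviations (Protocol 6.7) and by discontinuation for persistent noncompliance (Protocol 10.2). And AE dates are data known to be collected, whereas interruption dates are not a described field, so any narrower rule must infer them.

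**Conclusion.** The concern holds as a minor point. The SAP's date-window rule is wider than its stated purpose and can only raise percent compliance and the compliant count in subjects whose related AE required interruption. In the illustration it moves a subject from about 75–76% to 100%, across the 80% threshold. That size rests on the assumed 124 misses, all inside one long qualifying AE, and on a 4-application interruption. More or longer interruptions narrow the gap. The number of subjects affected cannot be derived from the documents.

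The consequences are contained. Compliance defines no analysis population (SAP 6.4.1 has only the Safety Population), there is no inferential testing (SAP 6.1), and the undeducted exposure measures remain visible. What is at risk is the compliance summary itself.

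**What to change.** In SAP 6.8.1:

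1. Report percent compliance and the compliant count twice, without any AE deduction and with the AE adjustment. Which one leads is a matter of preference.
2. For the adjusted figure, replace the onset-to-resolution window with the consecutive run of missed-application dates, taken from the dated dosing deviations, that falls within a related AE whose recorded action taken was interruption of study drug. End the run no later than the date of last application, which also settles AEs unresolved at exit.
3. State that this run is an approximation, because the protocol has interruptions recorded only as missed doses. Say how the run is chosen when one AE contains several, and whether a date with only one application missed belongs to it. Deducting every run inside the AE would restore the present rule.

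In SAP 8, note that the AE deduction is an addition to Protocol 11.3.

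The cost is SAP wording, a small programming change that needs no new data collection, and one extra table row. The adjusted compliant percentage may come out slightly lower.

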## 6.8.2 Adverse Events

AEs from ACN03/ACN04 will be included in the analysis for study ACN05. All AEs will be classified on the basis of Medical Dictionary for Regulatory Activities (MedDRA) terminology. Treatment-emergent AEs (TEAEs) are defined as AEs with an onset on or after the date of the first application of Olumacostat Glasaretil Gel, 5.0% (from ACN03/ACN04 or ACN05). If treatment-emergent status cannot be determined (e.g., unknown date of first application), the AE will be considered treatment-emergent. AEs noted prior to the first study drug administration that worsen after baseline will also be reported as AEs and included in the summaries.

TEAEs will be summarized in total as well as by 12-week periods based on time of onset in relation to date of first application of Olumacostat Glasaretil Gel, 5.0%, based on the definitions below.

- 0-12 Weeks            0 <= onset day <= 85
- >12-24 Weeks        86 <= onset day <= 169
- >24-36 Weeks        170 <= onset day <= 253
- >36 Weeks            onset day >= 254

Summaries will present the number of subjects reporting a TEAE by system organ class (SOC), preferred term, severity, relationship to study drug (causality), and seriousness. When summarizing TEAEs by severity and relationship, each subject will be counted once within a SOC or a preferred term by using the event with the greatest relationship or highest severity within each classification.

All information pertaining to an AE noted during the study will be listed by subject, detailing verbatim term given by the PI or designee, preferred term, SOC), onset date, resolution date, severity, seriousness, action taken, outcome and drug relatedness. The event onset will also be shown relative (in number of days) to date of first application.

Serious AEs (SAEs) will be summarized and listed using the same methodology as noted above. In addition, a listing of subjects who prematurely discontinued from the study due to an AE will be provided.

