## **8 STUDY PROCEDURES**

The procedures required for subject evaluation at each study visit are outlined below and in the study Schedule of Visits and Procedures (see [Appendix 1](#)). The timing of each study day is relative to the day of initial dosing (Baseline/Day 1). Visit windows are provided to allow study sites some flexibility in maintaining the study visit schedule for participating subjects. Out of window visits may be unavoidable in certain circumstances. Out of window visits are not considered deviations to the protocol.

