### 9.1 **Baseline/Day 1 Assessments**

The Baseline/Day 1 visit for this study occurs on the same day as the Week 12/study exit visit of the DRM01B-ACN03 or DRM01B-ACN04 visit. Therefore, if subjects choose to enroll in this study, study procedures will not be repeated; study sites will carry over the information from the DRM01B-ACN03 or DRM01B-ACN04 study to the Baseline/Day 1 visit for this study.

The study procedures that are to be carried over are:

- Demographic information: age, gender, race, ethnicity and Fitzpatrick Skin Type
- Medical history
- Adverse events
- Local skin reactions
- Concomitant medications
- Laboratory evaluations: hematology, serum chemistries and urinalysis
- Pregnancy testing
- 12-lead ECG
- Investigator Global Assessment of acne

- Photography (at selected sites)
- Vital signs and weight
- Acne Patient Self-Questionnaire

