#### **11.4 Adverse Events**

All AEs that occur during the study will be recorded and classified on the basis of Medical Dictionary for Regulatory Activities (MedDRA) terminology. Treatment-emergent AEs (TEAEs) are defined as AEs with an onset on or after the date of the first study drug application. Adverse events noted prior to the first study drug administration that worsen after baseline will also be reported as AEs and included in the summaries.

All information pertaining to an AE noted during the study will be listed by subject, detailing verbatim term given by the PI or designee, preferred term, system organ class (SOC), onset date, resolution date, severity, seriousness, action taken, outcome and drug relatedness. The event onset will also be shown relative (in number of days) to date of first application.

Treatment-emergent AEs will be summarized by treatment group, the number of subjects reporting a TEAE, SOC, preferred term, severity, relationship to study drug (causality), and seriousness. When summarizing AEs by severity and relationship, each subject will be counted once within a system organ class or a preferred term by using the event with the highest severity and greatest relationship within each classification.

Serious AEs will be summarized by treatment group, severity and relationship to study drug, and individual SAEs will be listed by subject. In addition, a list of subjects who prematurely discontinued from the study due to an AE will be provided.

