### **6. STATISTICAL AND ANALYTICAL PLANS**

#### **6.1 General Methodology**

All statistical processing will be performed using SAS® unless otherwise stated. Data will be summarized using descriptive statistics. No inferential testing or imputations for missing data will be performed.

Categorical variables will be tabulated with frequencies and percentages. Continuous variables will be tabulated with mean, median, SD, and range (minimum and maximum).

Reported AEs and prior and concomitant procedures and therapies will be classified on the basis of Medical Dictionary for Regulatory Activities (MedDRA) terminology. Concomitant medications will be classified on the basis of World Health Organization Drug Dictionary (WHO-DDE) terminology.

The following data will be imported from ACN03/ACN04 (Baseline defined in section 6.1.2):

Subjects receiving Olumacostat Glasaretil Gel, 5.0% in ACN03/ACN04:

- Demographic information: age, gender, race and ethnicity
- Prior and Concomitant medications
- Adverse events
- Local skin reactions (Baseline and Weeks 4, 8, 12)
- Vital signs and weight (Baseline and Weeks 4, 8, 12)
- Investigator Global Assessment of acne (Baseline and Week 12)
- Acne Patient Self-Questionnaire (Baseline and Week 12)
- Laboratory evaluations: hematology, serum chemistries and urinalysis (Baseline)
- 12-lead ECG (Baseline)

Subjects receiving Olumacostat Glasaretil Gel, Vehicle in ACN03/ACN04:

- Demographic information: age, gender, race, and ethnicity
- Prior and Concomitant medications
- Adverse events
- Local skin reactions (Baseline)
- Vital signs and weight (Baseline)
- Investigator Global Assessment of acne (Baseline)
- Acne Patient Self-Questionnaire (Baseline)
- Laboratory evaluations: hematology, serum chemistries and urinalysis (Baseline)
- 12-lead ECG (Baseline)

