### **6.1.2 Baseline Definition**

The baseline value for each parameter will be defined as the last observation prior to first dose of Olumacostat Glasaretil Gel, 5.0%. For subjects receiving Olumacostat Glasaretil Gel, 5.0% in ACN03/ACN04, the baseline values from ACN03/ACN04 will be considered the baseline values for calculations in ACN05. For subjects receiving Olumacostat Glasaretil Gel, Vehicle in ACN03/ACN04, baseline values will most commonly be from the Week 12/study exit visit of ACN03/ACN04. If subjects choose to enroll in this study, study procedures will not be repeated; study sites will carry over the information from the ACN03/ACN04 study to the Day 1 visit for this study.

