## 6.8 Safety Evaluation

### 6.8.1 Extent of Exposure

The extent of exposure to study drug in each treatment group will be summarized by total number of days of exposure, total number of applications, number of missed applications, amount of study drug used, amount of study drug per day, percent compliance and number and percentage of subjects who are compliant. A subject will be considered compliant with the dosing regimen if the subject applied 80-120% of the expected number of applications while enrolled in the study.

For subjects receiving Olumacostat Glasaretil Gel, 5.0% in ACN03/ACN04, the date of first application will be from ACN03/ACN04. For subjects receiving Olumacostat Glasaretil Gel, Vehicle in ACN03/ACN04, the date of first application will be from ACN05.

Total number of days of exposure will be computed as follows:

$$\text{Total Exposure} = \text{Date of Last Application} - \text{Date of First Application} + 1.$$

Dosing deviations reported for areas other than the face will not be considered in calculations. On the date of first application and the date of last application, some subjects were to apply one dose and others were to apply two doses, depending on the time of the study visit. After the date of first application and before the date of last application subjects were expected to apply two doses. Missed applications will be calculated from dosing deviations which report zero or one application on a given date. Extra doses will be calculated from dosing deviations which report more than the expected number of applications on a given date.

For subjects receiving Olumacostat Glasaretil Gel, 5.0% in ACN03/ACN04, the total number of applications will be the sum of the applications from ACN03/ACN04 and ACN05, as dosing deviations are specific to the dates of first and last application within each study. The methodology below will be applied to ACN03/ACN04 and ACN05 data separately, then summed.

The total number of applications will be calculated as follows:

If the Date of First Application is not equal to Date of Last Application, then

$$\begin{aligned} \text{Total Applications} &= 2 * (\text{Date of Last Application} - \text{Date of First Application} - 1) \\ &\quad + \text{Expected Applications on Date of First Application} \\ &\quad + \text{Expected Applications on Date of Last Application} \\ &\quad - \text{Missed Applications} + \text{Extra Applications.} \end{aligned}$$

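### For prior-vehicle subjects, an imported parent-study AE with onset dated to the first day of 5.0% gel counts as emergent on that gel, even if it was found before the gel was dispensed

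*SAP*

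**What the plan says.** SAP 6.8.2 states that TEAEs "are defined as AEs with an onset on or after the date of the first application of Olumacostat Glasaretil Gel, 5.0"%, counting from whichever study supplied that first application. Protocol 11.4 uses the same kind of date test: "Treatment-emergent AEs (TEAEs) are defined as AEs with an onset on or after the date of the first study drug application". Neither asks whether the event came before or after the dose on that date.

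SAP 6.8.2 also states that "AEs from ACN03/ACN04 will be included in the analysis for study ACN05". In SAP 6.1, the import list for "Subjects receiving Olumacostat Glasaretil Gel, Vehicle in ACN03/ACN04" limits LSRs, vital signs, IGA, questionnaire, laboratory data and ECG to Baseline, but lists adverse events with no limit by visit or date.

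On timing, Protocol 9.1 says "The Baseline/Day 1 visit for this study occurs on the same day as the Week 12/study exit visit" of the parent study. SAP 6.8.1 says "For subjects receiving Olumacostat Glasaretil Gel, Vehicle in ACN03/ACN04, the date of first application will be from ACN05". On baseline for these subjects, SAP 6.1.2 says "baseline values will most commonly be from the Week 12/study exit visit of ACN03/ACN04", having defined baseline by order relative to the first 5.0% dose.

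Two more sentences follow the TEAE definition in SAP 6.8.2. One counts an AE as treatment-emergent when its status cannot be determined. The next brings in AEs seen before first administration when they later worsen.

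**The concern.** A rule that counts everything from the first-dose date onward is usually harmless, because a pre-dose finding on that day goes to medical history. That safeguard is weak here. A prior-vehicle subject reaches Day 1 from a treated study, so something found at the Week 12 visit may already be an AE in the parent database, and the SAP imports it.

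One finding could then be both the subject's pre-dose baseline and an event emergent on 5.0% gel. The two SAP sections use different tests for the same day: 6.1.2 uses dose order and 6.8.2 uses the calendar date. Within 6.8.2, the sentence on worsening also points to dose order. A programmer would have to choose, and the choice changes the count.

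At stake is the first-12-week TEAE summary for prior-vehicle subjects, the group whose whole 5.0% exposure falls inside ACN05. Events that began on vehicle could enter that summary.

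**Working it through.** The plan gives no figure on this point, so the check applies its rules to the possible orders of event and first dose.

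**Inputs**
- TEAE test: onset date on or after the first 5.0% application date (SAP 6.8.2).
- First-application date for prior-vehicle subjects: from ACN05 (SAP 6.8.1).
- Day 1 is the day of initial dosing (Protocol 8) and the parent Week 12 date (Protocol 9.1). ACN05 drug is dispensed at that visit (Protocol 8.1), and one or two doses are expected that day depending on visit time (SAP 6.8.1). A same-day first application is therefore the expected case.
- Study day: date difference plus 1 on or after Day 1; plain difference before it (SAP 6.1.3).
- First onset window: days 0 to 85 (SAP 6.8.2).

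**Five timings for a prior-vehicle subject**

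| Onset as recorded | First 5.0% gel | Study day | SAP rule | True order |
|---|---|---|---|---|
| Week 12 day, found at the visit | Same day, after the visit | 1 | TEAE | Before gel |
| 3 days before the visit | Visit day | -3 | Not TEAE | Before gel |
| Week 12 day | Next day | -1 | Not TEAE | Before gel |
| Week 12 day, after applying gel | Visit day | 1 | TEAE | After gel |
| Next day | Visit day | 2 | TEAE | After gel |

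Only the first row is misclassified. Its onset day is 1 by the study-day formula (0 + 1) or 0 by simple difference; both lie in 0 to 85, so the event falls in the 0-12 week period. A strict rule requiring onset after the first-application date would correct row 1 but wrongly drop row 4, a true post-dose event.

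Prior-active subjects are not affected at this visit, because their first-application date lies in the parent study.

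**Size.** Two quantities are needed and neither is in the documents: the prior-vehicle share of enrolment, and the proportion of those subjects with an AE dated to the Week 12 day. Purely as an illustration, assume a share of one third to one half of 700 and a proportion of 0.5% to 5%:
- Low: 700 x 1/3 = 233; 233 x 0.005 = 1.2 subjects; 1.2/700 = 0.2%.
- High: 700 x 1/2 = 350; 350 x 0.05 = 17.5 subjects; 17.5/700 = 2.5%.

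The width of that range comes from the assumptions. It is not an estimate.

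**The case against.** The best defence is that the plan already points the right way. The sentence on AEs that worsen implies that an unchanged pre-dose AE is not meant to count. That is a fair reading of intent, but it only adds events to the summaries; it does not say that a same-date pre-dose AE is removed, and the explicit definition still includes it. It makes the fix a clarification between neighbouring sentences.

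Protocol 9.4.7 sends events before treatment to medical history. That governs entry in the ACN05 eCRF. It does not filter AEs imported from the parent database, and Protocol 9.1 has sites carry adverse events over to Day 1.

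Protocol 5.3.2 keeps out subjects whose Week 12 examination, vital-sign or ECG findings contraindicate further treatment in the investigator's judgment. This removes some examples, but the criterion does not name laboratory results or LSRs.

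The parent protocols are not available. That a Week 12 finding becomes an AE dated to that visit is inferred from the ACN05 rules in Protocol 9.4.2, 9.4.4 and 9.4.5, which cover new or worsened clinically significant findings and LSRs scored 3. This objection stands, and it is why the frequency cannot be known.

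Finally, the error is conservative, the study is descriptive with no inferential testing, and the AE listing shows onset day relative to first application, so same-day events can be seen. All of that stands and limits the consequence. It does not make the tabulated classification correct.

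**Conclusion.** The concern holds in a narrow form. In prior-vehicle subjects the SAP's date test classes an imported parent-study AE as emergent on 5.0% gel when its recorded onset date equals the first-application date, even if it was found at the Week 12 assessments before any 5.0% gel was dispensed. This conflicts with SAP 6.1.2 and sits badly with the worsening sentence in 6.8.2. It touches only the prior-vehicle and all-subject columns of the 0-12 week period, and the overall count that contains it. The bias is conservative and probably small, and its size cannot be derived from the documents.

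Three stronger readings are not supported:
- A reader might infer that everything found or reported at the Week 12 visit is charged to 5.0% gel. Events with an earlier recorded onset, or with first application on a later day, are classified correctly.
- A reader might infer that parent AEs with partial onset dates are also swept in by the default for undetermined status. The SAP's only example is an unknown first-application date, and it states no rule for partial AE onset dates. Counting a truly undeterminable event as emergent is also a defensible conservative choice.
- A reader might want a count of misclassified subjects. Any such number is an assumption.

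The conclusion rests on the expected same-day first application and on Week 12 findings being recorded in the parent study as AEs with that onset date.

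**What to change.** Add to SAP 6.8.2: for subjects who received vehicle in ACN03/ACN04, an AE recorded in the parent study, including one carried over to ACN05 Day 1 from the Week 12 visit, whose onset date equals the ACN05 first-application date is not treatment-emergent unless it worsened after that application or is documented as starting after it.

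State also what does not change. All AEs with a later onset date, AEs first recorded in ACN05 with onset on Day 1, and AEs whose order relative to the first dose truly cannot be determined remain treatment-emergent. The current rule stays for prior-active subjects. Flag the reclassified events in the AE listing so that a reader can restore them.

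The rule should not exclude every parent-recorded AE regardless of onset date. That could hide an event that began after 5.0% gel but was entered in the parent eCRF. Nor should the eCRF alone decide: a Week 12 AE carried over to Day 1 would then be counted again.

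The cost is a source-study flag in the AE dataset and a short addition to the SAP, with no new data. The downside is slightly fewer events counted on 5.0% gel, which the listing flag keeps visible.
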